5.5.8 Treatment of Nivolumab or Ipilimumab Related Infusion Reactions

Since nivolumab and ipilimumab contain only human immunoglobulin protein sequences, it is unlikely to be immunogenic and induce infusion or hypersensitivity reactions. However, if such a reaction were to occur, it might manifest with fever, chills, rigors, headache, rash, pruritis, arthralgias, hypo- or hypertension, bronchospasm, or other symptoms.

All Grade 3 or 4 infusion reactions should be reported as an SAE if criteria are met. Infusion reactions should be graded according to NCI CTCAE (Insert version e.g.: 4.0) guidelines.

Treatment recommendations are provided below and may be modified based on local treatment standards and guidelines as appropriate:

For Grade 1 symptoms: (Mild reaction; infusion interruption not indicated; intervention not indicated)

Remain at bedside and monitor subject until recovery from symptoms. The following prophylactic premedications are recommended for future infusions: diphenhydramine 50 mg (or equivalent) and/or paracetamol 325 to 1000 mg (acetaminophen) at least 30 minutes before additional nivolumab administrations.

For Grade 2 symptoms: (Moderate reaction requires therapy or infusion interruption but responds promptly to symptomatic treatment [eg, antihistamines, non-steroidal anti inflammatory drugs, narcotics, corticosteroids, bronchodilators, IV fluids]; prophylactic medications indicated for 24 hours).

Stop the nivolumab or ipilimumab infusion, begin an IV infusion of normal saline, and treat the subject with diphenhydramine 50 mg IV (or equivalent) and/or paracetamol 325 to 1000 mg (acetaminophen); remain at bedside and monitor subject until resolution of symptoms. Corticosteroid or bronchodilator therapy may also be administered as appropriate. If the infusion is interrupted, then restart the infusion at 50% of the original infusion rate when symptoms resolve; if no further complications ensue after 30 minutes, the rate may be increased to 100% of the original infusion rate. Monitor subject closely. If symptoms recur then no further nivolumab or ipilimumab will be administered at that visit. Administer diphenhydramine 50 mg IV, and remain at bedside and monitor

the subject until resolution of symptoms. The amount of study drug infused must be recorded on the electronic case report form (eCRF). The following prophylactic premedications are recommended for future infusions: diphenhydramine 50 mg (or equivalent) and/or paracetamol 325 to 1000 mg (acetaminophen) should be administered at least 30 minutes before additional nivolumab or ipilimumab administrations. If necessary, corticosteroids (recommended dose: up to 25 mg of IV hydrocortisone or equivalent) may be used.

For Grade 3 or Grade 4 symptoms: (Severe reaction, Grade 3: prolonged [ie, not rapidly responsive to symptomatic medication and/or brief interruption of infusion]; recurrence of symptoms following initial improvement; hospitalization indicated for other clinical sequelae [eg, renal impairment, pulmonary infiltrates]). Grade 4: (life threatening; pressor or ventilatory support indicated).

Immediately discontinue infusion of nivolumab or ipilimumab. Begin an IV infusion of normal saline, and treat the subject as follows. Recommend bronchodilators, epinephrine 0.2 to 1 mg of a 1:1,000 solution for subcutaneous administration or 0.1 to 0.25 mg of a 1:10,000 solution injected slowly for IV administration, and/or diphenhydramine 50 mg IV with methylprednisolone 100 mg IV (or equivalent), as needed. Subject should be monitored until the investigator is comfortable that the symptoms will not recur. Nivolumab or ipilimumab will be permanently discontinued. Investigators should follow their institutional guidelines for the treatment of anaphylaxis. Remain at bedside and monitor subject until recovery from symptoms. In the case of late-occurring hypersensitivity symptoms (eg, appearance of a localized or generalized pruritis within 1 week after treatment), symptomatic treatment may be given (eg, oral antihistamine, or corticosteroids).

5.5.9 Treatment Beyond Progression

Accumulating evidence indicates a minority of subjects treated with immunotherapy may derive clinical benefit despite initial evidence of PD.

Subjects will be permitted to continue treatment beyond initial RECIST 1.1 defined PD as long as they meet the following criteria:

- Investigator-assessed clinical benefit and subject is tolerating study drug.

The assessment of clinical benefit should take into account whether the subject is clinically deteriorating and unlikely to receive further benefit from continued treatment.

Subjects should discontinue study therapy upon further evidence of further progression, defined as an additional 10% or greater increase in tumor burden volume from time of initial progression (including all target lesions and new measurable lesions). New lesions are considered measurable at the time of initial progression if the longest diameter is at least 10 mm (except for pathological lymph nodes, which must have a short axis of at least 15 mm). Any new lesion considered non-measurable at the time of initial progression may become measurable and therefore included in the tumor burden measurement if the longest diameter increases to at least 10 mm (except for pathological lymph nodes, which must have an increase in short axis to at least 15 mm).

However, given the uncertainties around defining progression versus pseudoprogression during immunotherapy, treatment will be allowed to be continued beyond protocol-defined progression if, in the judgment of the treating physician, further benefit to the patient is possible with continuation of

therapy. For statistical analyses, this will need to be described in patient population information. E.g. Subjects who continue treatment beyond initial investigator-assessed, RECIST 1.1-defined progression will be considered to have investigator-assessed progressive disease at the time of the initial progression event.

5.6 Treatment Compliance

Treatment compliance will be monitored by drug accountability as well as the subject's medical record and eCRF.

5.7 Destruction of Study Drug

For this study, study drugs (those supplied by BMS or sourced by the investigator) such as partially used study drug containers, vials and syringes may be destroyed on site.

Any unused study drugs can only be destroyed after being inspected and reconciled by the responsible Study Monitor unless study drug containers must be immediately destroyed as required for safety, or to meet local regulations (eg, cytotoxics or biologics).

On-site destruction is allowed provided the following minimal standards are met:

- On-site disposal practices must not expose humans to risks from the drug.
- On-site disposal practices and procedures are in agreement with applicable laws and regulations, including any special requirements for controlled or hazardous substances.
- Written procedures for on-site disposal are available and followed. The procedures must be filed with the site's standard operating procedures (SOPs) and a copy provided to BMS upon request.
- Records are maintained that allow for traceability of each container, including the date disposed of, quantity disposed, and identification of the person disposing the containers. The method of disposal, ie, incinerator, licensed sanitary landfill, or licensed waste disposal vendor must be documented.
- Accountability and disposal records are complete, up-to-date, and available for the Monitor to review throughout the clinical trial period.

6 RADIATION THERAPY

Metastatic lesions with the following distribution are eligible to be treated with SBRT on this protocol:

1 – 4 metastases distinct from the measurable target lesion that will not be irradiated to evaluate responses to the abscopal effect and immunotherapy. Larger lesions are given preference for SBRT to maximize tumor antigen release. The irradiated lesion will not be included in the calculations for measurable disease.

SBRT will be given Week 2 - 3, please see Section 5.5 and 6. SBRT should begin Week 2, and therefore, the radiation planning process should begin as the patient is registered for the study prior to randomization. SBRT for all metastases should be completed within 2 weeks of the first dose of SBRT. Not all metastases need to receive radiation therapy on the same day.

Most commercially available photon producing treatment units are allowed. As such, conventional linear accelerators, specialized linear accelerators with image guidance (e.g., Novalis, Trilogy, Synergy, Artiste, TrueBeam) are allowed. These units can be used with conformal dose delivery or IMRT. Specialized dose painting accelerators (e.g., Cyberknife, Gammaknife or Tomotherapy) are allowed provided they meet the technical specifications of the protocol and are used in a fashion that passes the credentialing required by the protocol. Conventional linear accelerators without add-on IGRT must have some other IGRT capability like CT-on-rails in the treatment room.

IGRT is required for this study. Either 3DCRT or IMRT (including VMAT) are all acceptable planning techniques. Planning techniques may differ for each lesion to be treated provided that the tumor motion is properly accounted for with each technique when the target or targets are in or near the thorax region.

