- To assess the overall safety and tolerability of nivolumab and ipilimumab versus SBRT plus nivolumab and ipilimumab in subjects with metastatic Merkel cell carcinoma.
- To evaluate whether PD-L1 expression is a predictive biomarker for ORR.
- To evaluate the Health Related Quality of Life (HRQoL) as assessed by European Organisation for Research and Treatment of Cancer (EORTC) QLQ-C30.

Exploratory: See [Section 1.3.3](#) of the protocol.

Study Design:

This is a Phase 2, randomized, multi-institutional study of nivolumab and ipilimumab alone versus in combination with SBRT for subjects (≥ 18 years) with metastatic Merkel Cell Carcinoma. Approximately 50 subjects will be randomized 1:1 and stratified by prior immunotherapy exposure. Dose reductions will not be allowed.

Treatment Arms:

Randomized 1:1 [Arm A: Arm B]: Treatment until progression on either arm.

Arm A:

Nivolumab 240 mg IV over 30 min q2 weeks and Ipilimumab 1 mg/kg IV over 30 min q6 weeks until progression or unacceptable toxicity

Arm B:

Nivolumab 240 mg IV over 30 min q2 weeks and Ipilimumab 1 mg/kg IV over 30 min q6 weeks until progression or unacceptable toxicity

Radiation to be given at the start of week 2

- 8 Gy x3 doses in over ≤ 2 weeks

SBRT should begin the week following the first dose of nivolumab and ipilimumab. All sites other than skin should receive SBRT in consecutive days. Skin lesions can be treated every other day.

The number of lesions receiving SBRT will be at the treating physician's discretion based on anticipated toxicity. Larger or symptomatic lesions are of higher priority for SBRT. At least one target lesion will not receive SBRT, to evaluate ORR. The scatter radiation dose to this target lesion should be monitored if located less than 6cm from the irradiated lesions.

All subjects will be treated until progression of disease, unacceptable toxicity, or subject withdrawal of consent. Palliative radiation therapy will not be permitted while being treated under the protocol. The need for palliative radiation therapy will be considered progressive disease.

Study Population: Metastatic Merkel cell carcinoma subjects

Key Inclusion Criteria:

- At least 18 years of age
- ECOG PS < 2
- Active disease measurable by CT or MRI.
- Prior chemotherapy or immunotherapy will be allowed if new or persistent measurable site(s) of disease are present.
- Prior radiation therapy will be allowed if there is active measurable disease burden.

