1.2.4 Summary

We have a compelling rationale for combining Ipilimumab and SBRT with Nivolumab for metastatic MCC with our preliminary data suggesting a potential abscopal effect of radiation therapy in MCC potentiated by Ipilimumab, and expression of PD-L1 in the majority of MCC patients. Poor prognosis associated with metastatic MCC requires development of a new and effective therapeutic modality.

Therefore, we propose to further augment the therapeutic efficacy of PD1 blockade in patients with metastatic Merkel cell carcinoma by the abscopal effect of stereotactic body radiation therapy (SBRT) and another immune checkpoint inhibitor, ipilimumab to boost immune priming. The optimal sequences of immunotherapy to partner with SBRT to maximize the efficacy of combined treatment remain elusive, and this study will allow for direct comparison of the clinical benefit, as measured by objective response rate, provided by the addition of SBRT to nivolumab and ipilimumab in MCC.

Finally, the proposed clinical trial is strategically designed to define the standard treatment regimens for metastatic Merkel cell carcinoma with acceptable toxicity. The insights on the synergy of SBRT, Nivolumab and Ipilimumab drawn from Merkel cell carcinoma will be applicable to other solid cancers.

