1.3 Objectives(s)

1.3.1 Primary Objectives

- To compare the efficacy, as measured by ORR, provided by nivolumab and ipilimumab versus

SBRT plus nivolumab and ipilimumab in subjects with metastatic Merkel cell carcinoma.

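### ORR is scored on non-irradiated target lesions, but the plan neither fixes the target set before randomisation nor gives Arm A a matching step, so the between-arm difference may not isolate SBRT

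*Combined protocol and SAP*

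**What the plan says.** Section 1.3.1 makes the randomised comparison the primary objective ("To compare the efficacy, as measured by ORR, provided by nivolumab and ipilimumab versus" the same drugs plus SBRT). Section 1.2.4 says that "this study will allow for direct comparison of the clinical benefit, as measured by objective response rate, provided by the addition of SBRT" to the two drugs.

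On the lesions that count:

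- Section 6: SBRT goes to one to four "metastases distinct from the measurable target lesion that will not be irradiated to evaluate responses to the abscopal effect and immunotherapy". It adds: "Larger lesions are given preference for SBRT to maximize tumor antigen release", and "The irradiated lesion will not be included in the calculations for measurable disease".
- Synopsis, Treatment Arms: "The number of lesions receiving SBRT will be at the treating physician's discretion based on anticipated toxicity". Larger or symptomatic lesions have priority. "At least one target lesion will not receive SBRT, to evaluate ORR".
- Sections 6.5.4 and 9.2.1: the primary endpoint is response of non-irradiated target lesions. Section 6.5.4 gives the reason, which is to keep direct radiation effects out of the scored lesion.
- Section 6, on timing: "the radiation planning process should begin as the patient is registered for the study prior to randomization".
- Section 5: the study is not blinded.

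No place names the lesions that would have been irradiated in an Arm A patient, or says when target lesions are designated. The randomisation inputs (5.4), the screening table (Table 7.1-1), the efficacy and measurement rules (7.4 to 7.4.2) and Section 9 are all silent on it.

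**The concern.** The phrase non-irradiated target lesions covers both arms, but in Arm A it removes nothing. In Arm B it can remove up to four lesions, and these are not a random pick. Take a patient with two measurable lesions, the minimum number of lesions for entry. In Arm B the patient may be scored on the smaller one alone. In Arm A the same patient may be scored on both.

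Randomisation balances patients. It does not balance a lesion selection made for one arm only. If lesions within a patient respond differently, and the difference is related to size or symptoms or is simply variable, the two ORRs can differ with no SBRT effect at all, even when the protocol is followed exactly. What is at stake is the reading of the primary comparison, not the conduct of either arm.

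**Working it through.** **1. The plan's own figures.** Inputs from Section 9.1.1: stage 1 has 16 patients per arm and continues with 3 or more responses; stage 2 brings the total to 24 and passes with 7 or more; if both arms pass, B wins when Pr(B>A) > 0.8 under beta(1,1) priors.

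Pass(p) = P(X1 ≥ 3 and X1 + X2 ≥ 7), with X1 ~ Bin(16, p) and X2 ~ Bin(8, p). This gives Pass(0.17) = 0.0978 and Pass(0.40) = 0.9013.

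P(B wins) = Pass(pB) × [1 − Pass(pA)] + P(both pass and Pr(B>A) > 0.8).

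| True B / A | Only B passes | Both pass, B chosen | P(B wins) | Plan |
|---|---|---|---|---|
| 40 / 17 | 0.9013 × 0.9022 = 0.813 | 0.041 | 85.4% | 85% |
| 17 / 17 | 0.0978 × 0.9022 = 0.088 | 0.0003 | 8.8% | 8.89% (simulated) |
| 40 / 40 | 0.9013 × 0.0987 = 0.089 | 0.158 | 24.7% | not given |

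The plan's figures reproduce. They take it that the measured ORR means the same thing in both arms. About 81 of the 85 power points come from B passing its gate while A fails.

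**2. Can the lesion set alone change a patient's status, and which way?** Assume one 60 mm and one 20 mm lesion, the larger irradiated in Arm B, and response defined as a fall of at least 30% in the sum of diameters.

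- Large −10%, small −50%: all lesions (54 + 10)/80 − 1 = −20%, no response; small lesion alone −50%, response.
- Large −45%, small unchanged: all lesions (33 + 20)/80 − 1 = −34%, response; small lesion alone 0%, no response.

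Both directions are possible.

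**3. What a shift does to the decision.** With no SBRT effect and Arm A at 17%, a shift of +5 points in Arm B's measured ORR raises P(B wins) from 8.8% to 23.7%; −5 points lowers it to 1.7%. With Arm A at 40%, the same shifts give 36.2% and 15.7% instead of 24.7%.

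**4. A lesion model, for scale only.** Every input here is assumed, because the documents hold no lesion-level data:

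- Lesion size: lognormal, median 25 mm, log-SD 0.5, floor 10 mm.
- Log size change: mean + patient effect (SD 0.5) + lesion effect (SD 0, 0.3 or 0.4) + slope (−0.15, 0 or +0.15) × centred log size.
- The largest lesions are irradiated; response is CR+PR by the 30% rule; there is no SBRT effect.
- The mean is set so that Arm A's ORR on all lesions is 40% or 17%.

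| Lesions / irradiated | P(B wins), Arm A at 40% | P(B wins), Arm A at 17% |
|---|---|---|
| Lesions respond alike | 24.7% | 8.8% |
| 2/1 or 4/2 | about 16–40% | about 3.6–29% |
| Adding 5/4 | about 11–56% | about 2–54% |

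The outer limits in the last row arise only with five lesions of which four are irradiated. Arm B's ORR falls if larger lesions shrink more, and rises if they shrink less or if lesions merely vary.

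**5. What matching does.** Over all these settings, computing Pr(B>A) on the matched set with the gates unchanged brings P(B wins) at the 40% base to 22.5–28.7%. At the 17% base the range hardly moves (1.8–54.5% before, 1.8–54.0% after), because both arms rarely pass and the gates decide.

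**The case against.** The strongest reply is that there may be no mismatch. Section 6 describes SBRT lesions as distinct from the measurable target lesion, Table 7.1-1 puts the baseline efficacy assessment in screening, and radiation planning starts before randomisation. If targets are named then and SBRT goes only to other lesions, both arms are scored on targets chosen without knowledge of allocation. This stands as a possible reading, so the mismatch is not certain. The documents do not establish it. The Synopsis asks only that at least one target lesion be spared, which allows others to be irradiated. Section 7.4 ties the baseline assessment to the first dose, which may follow randomisation by up to two weeks. Nothing requires a lesion list to be recorded.

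Second, leaving irradiated lesions out is deliberate and sensible for an abscopal question. That stands in full; the gap is only the missing counterpart in Arm A.

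Third, the model in step 4 is invented, its extremes come from one setting, and it omits confirmation of response, new lesions, and selection by symptoms or anticipated toxicity. That also stands, and the ranges are not estimates.

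Fourth, the remedy scarcely moves P(B wins) at the design's null rate. That is true. Its value there lies in interpretation.

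A reader might infer that the arms are bound to be scored on different lesions, or that the rule favours SBRT because smaller lesions are left. The documents support neither. They give no response rates by lesion size or symptoms, and if larger lesions shrink more the bias runs against Arm B.

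**Conclusion.** The concern holds as a gap in the definition of the primary comparison. The plan does not ensure that ORR is read on comparable lesions in the two arms, so an observed difference may not be due to SBRT alone. The bias is zero under either of two conditions: lesions within a patient respond alike, or targets are designated before allocation and only non-target lesions are irradiated. Outside these, direction and size cannot be had from the documents. The 16–40% and 3.6–29% ranges show only that modest assumed differences between lesions could matter under the plan's own decision rule; they rest on the step 4 model, no SBRT effect and CR+PR scoring. The change is worth making because it is cheap and the comparison concerned is the primary objective.

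**What to change.** First reconcile the endpoint: the Synopsis (Study Assessments) counts complete and partial response, while Sections 9.2.1 and 9.3.2.1 also count stable disease.

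Then amend Sections 6 and 9.2.1, with a matching line where Section 9.1.1 defines Pr(B>A):

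- Before randomisation, the site records for every patient (i) the lesions that would receive SBRT if the patient were assigned to Arm B, and (ii) the remaining target lesions.
- The between-arm ORR comparison, including Pr(B>A), uses set (ii) as recorded, in both arms.
- The two Simon gates and the winner rule stay. Beside any win decided by the gates alone, report the set (ii) ORR difference and state that such a win does not by itself isolate the SBRT effect. Say plainly that this does not alter P(B wins) when the gates decide.
- The record does not bind treatment. If a set (ii) lesion is irradiated, report how often and add a sensitivity analysis, since this can happen only in Arm B.
- For patients already randomised, apply a stated size-based rule to baseline scans, identically in both arms and blind to outcome, as a sensitivity analysis only. It cannot recover choices that turned on symptoms or discretion. Accrual status is not stated in this version 11; if accrual is complete, this is the only part still available.

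Cost: one CRF item at a planning step that already precedes randomisation, the amendment, a re-run of the Section 9.1.1 simulation, fewer scored lesions in Arm A for the comparison, and two Arm A ORR figures to explain. No treatment rule changes.

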6.1 Dose Specification

6.1.1 Dose Fractionation

Patients will receive 24Gy in 3 fractions of radiation in 3 consecutive days for non-skin lesions. Skin lesions are allowed to be treated every other day. Simultaneous integrated boost or dose-painting will be allowed to meet normal tissue dose constraints. If dose-painting is utilized, we recommend V21Gy > 90% of GTV and V24Gy > 1cc. This dose is well below the standard dose fractionation employed by SBRT in various disease locations ranging from 30Gy to 45Gy in 3 fractions, which have been deemed safe on available evidence and/or expert consensus in each disease site. Therefore we do not anticipate treatment related toxicity.

6.1.2 Technical Factors

6.1.2.1 Physical Factors

Only photon (x-ray) beams with photon energies ≥ 6 MV will be allowed with the exception of radiation therapy to the skin for which electron beams will be allowed. For metastases located within 3 cm of the lungs, photon energies of 6-10 MV are required. For lung central and lung peripheral metastases, photon beam energies > 10 MV are allowed only for a limited number ($\leq 50\%$ of all beams or all beam angles) of beams that must travel more than a cumulative distance of 10 cm through soft tissue (not lung) to reach the isocenter OR a shorter distance if the tumor abuts the chest or abdominal wall (i.e., to spare skin dose).

FFF photon beams are allowed if the institution has performed SBRT credentialing with FFF beams.

Minimum Field Aperture (Field Size) Dimension

Because of uncertainties in beam commissioning resulting from electronic disequilibrium within small beam apertures, in general an equivalent square field dimension of 3 cm is recommended for fields used for treatment delivery for sites using standard 3-D conformal techniques where nearly all of the PTV is encompassed for each beam. It is understood that this may exceed the technical requirements for small lesions. In such cases, the prescription dose is still prescribed to the edge of the defined planning treatment volume (PTV). For sites using dose painting including IMRT techniques, where by design the entire PTV is not encompassed for each beam, smaller beam apertures are allowed.

All institutions must use heterogeneity correction algorithms approved by IROC Houston independent of the treatment planning technique. All doses should be reported in terms of dose-to-water and not in terms of dose-to-medium.

Stereotactic Targeting

For the purposes of this protocol, the term ‘stereotactic’ implies the targeting, planning, and directing of radiation beams along any trajectory in 3-D space toward a target of known 3-D coordinates. The coordinate system is defined by reliable ‘fiducials.’ A fiducial may be external or internal to the patient’s body. External fiducials may relate to a frame or treatment device.

Internal fiducials may be implanted markers OR reliably identifiable anatomy that is clearly visible on orthogonal kV imaging including the tumor itself. In all cases, the relationship between the fiducial and the actual tumor position in real time should be reliably understood for both planning and treatment.

Isocenter Placement

When using a gantry mounted linear accelerator for this protocol, the isocenter is defined as the common point of gantry, collimator, and couch rotation for the treatment unit. For other types of treatment units (e.g., Tomotherapy or CyberKnife), a reference point in space that is typically positioned at the center of the target is used instead of a mechanical isocenter.

When treating multiple lesions, it is best to use multiple isocenters, each centered on a separate lesion. Treating different targets on different days is allowed in order to decrease treatment time for a single day. For widely spaced lesions (over 10 cm apart), localization is improved when the isocenter is placed in the center of each target and image guidance is performed individually for each target. This is due to the limitation of most IGRT systems which ignore necessary rotational corrections when table shift coordinates are derived. Some platforms, including Cyberknife and Tomotherapy, are inherently non-isocentric. These platforms take special account in the setup and treatment process to rigorously detect and account for rotations to avoid errors making them exempt from the separate isocenter for each lesion requirement. For other platforms, the use of a single isocenter to treat multiple lesions in proximity to each other may be allowed if the institution has credentialed successfully for SBRT treatment of 2 lesions with a single isocenter setup.

Composite Dose Calculations

Composite plans should be generated to incorporate the dose to surrounding normal tissues from each metastasis treated. The composite doses to critical normal tissues will be used to evaluate plan compliance. Composite planning refers to dose summation from multiple treatment sites on a single CT scan that encompasses the relevant anatomy. Composite treatment planning is best accomplished by obtaining a planning CT dataset that incorporate all targets and relevant critical structures in the imaging study. If this is not possible due to restrictions on the size of the imaging study that can be

managed by the treatment planning system, CT datasets should be divided into two parts and treatment fields should be adjusted so that dose spillage from the treatment of targets in one dataset to the next is minimal such that the dose contributions do not require summation. The two datasets should be obtained so that they have some amount of overlap that can be used to fuse the information using a rigid registration technique. The use of deformable registration to sum dose is not allowed. In general, it is best to perform CT scanning with the patient in the same position. This implies that, for example, all lesions planned on a gated CT scan must be treated with gating. If technical limitations are encountered in summing dose, contact the PI with questions regarding composite planning.

Localization, Simulation, and Immobilization

Patient Positioning (Immobilization)

Patients will be positioned in a stable position capable of allowing accurate reproducibility of the target position throughout treatment. Positions uncomfortable for the patient should be avoided so as to prevent uncontrolled movement during treatments. Patient immobilization must be reliable enough to ensure that the gross tumor volume (GTV) does not deviate beyond the confines of the planning treatment volume (PTV). Positioning patients on flat couches and relying solely on image-guidance for reproducible set-up is strongly discouraged.

Simulation

All patients will undergo CT-based treatment planning in custom made immobilization devices. CT scan range must allow simultaneous view of the patient anatomy and fiducial system for stereotactic targeting (if used) and be adequate to ensure contouring of all targeted metastases, as well as necessary organs at risk (OAR), defined below. High-resolution CT scans should be obtained with uniform slice thickness of $\leq 3\text{mm}$ (ideally 1 – 2 mm) throughout. If a single CT scan cannot be obtained due to a large spatial separation between metastases (i.e., cervical and femoral metastases), or planning system slice number limitation, multiple CT scans are allowed provided that OAR are entirely encompassed in a single CT scan. CT imaging should be performed so that a composite dose distribution including all treated metastases can be created. Ideally all metastases will be treated in one treatment position. When treating multiple metastases such as a lung and extremity, varying the treatment position may be necessary (i.e. simulation with arms up and arm to the side). Thus, more treatment positions can be used at the discretion of the treating oncologist, but every effort should be made to obtain a composite distributions.

The use of IV contrast is required for liver metastases. For other metastases (central & peripheral lung, cervical/mediastinal, abdominal-pelvic, and spinal/paraspinal), the use of IV contrast is encouraged but will be left to the discretion of the treating physician. The use of other contrast agents is left to the discretion of the treating oncologist. Planning datasets without intravenous contrast may be used for dose calculation.

The use of bolus is required for skin primary disease or metastases. The thickness of bolus should ensure adequate coverage of the involved skin.

Respiratory Motion Assessment and Management

All metastases with potential for respiratory motion should be evaluated by appropriate means including 4D CT scan, implanted fiducial marker, or fluoroscopy at the time of simulation. Respiratory motion management (RMM) including abdominal compression, active breathing control, breath hold, end expiratory gating, or fiducial marker tracking, is recommended for any metastasis to be treated with motion $> 5\text{mm}$. A recommended approach would be to use an ITV technique for motion $< 1\text{cm}$, but for motion $> 1\text{cm}$ (typically too large for a free breathing ITV) motion management including but

not limited to abdominal compression, active-breathing control (ABC), gating, breath hold, etc. should be used.

If a treatment for multiple metastases (i.e., lung and spine) is designed on a CT scan employing motion management (i.e., abdominal compression), all metastases should be treated with the chosen motion management technique in order to generate an accurate composite dose calculation.

Localization Using Daily IGRT

As an SBRT protocol, this study requires the use of IGRT. NRG Oncology defines IGRT as a computer assisted process that uses imaging devices that generate a series of coordinates for shifting the patient support system in three orthogonal directions (sometimes including rotational changes) to position the treatment beams relative to target regions. The allowed technologies are as follows: cone-beam CT (CBCT) using either a specially mounted kV imaging head or the MV treatment beam with an opposed electronic imaging panel, dual fixed-position in-room kV imaging systems that are orthogonal or near orthogonal, an in-room standard diagnostic CT scanner that is geometrically linked to the treatment unit, and the Tomotherapy approach.

Although all of these units are allowed, some might not be appropriate for some disease sites. For example, orthogonal imaging techniques result in overlapping structures that are not as easily visualized compared to 3D cone-beam approaches. Simple portal imaging approaches that do not use computer assistance are not considered to be suitable for this study.

When the treatment equipment is not equipped with any device that allows direct visualization of anatomical structures using the treatment beam, the recommendations of AAPM Task Group Report 142 for testing the coincidence of the imaging and treatment reference points must be implemented. For example, verification of treatment and imaging isocenter coincidence must be performed routinely for the CyberKnife, Tomotherapy units as well as any BrainLab equipment that does not include an electronic portal imaging device (EPID) that intercepts the treatment beam.

The minimum IGRT requirement for each metastatic location is listed in Table 6-2. Volumetric imaging refers to 3D modalities (e.g., kV cone-beam, MV cone-beam, CT on rails) while orthogonal imaging refers to 2D modalities (e.g., kV OBI, ExacTrac). For volumetric imaging, appropriate CT window/level thresholds must be employed for registration at each metastatic location as outlined in Table 6-3. Additional IGRT may be employed at the discretion of the treating physician (i.e., orthogonal kV imaging prior to required volumetric imaging or volumetric imaging even if only orthogonal kV imaging is required). Note that when orthogonal kV imaging is employed for sites where respiratory motion is expected and not controlled via motion management techniques, care must be taken to ensure accurate targeting of the ITV within the treatment. For example, static kV imaging at an undetermined breath hold position would not be adequate IGRT for treating a free-breathing lung tumor.

Use of a shortened CT planning scan for registration may be important for IGRT systems that cannot handle a large number of CT slices. A subset of the planning CT scan can be uploaded to the IGRT system for localization of each metastasis. The CT data should include the metastasis of interest plus at least 5cm superiorly and inferiorly. Please note that composite dose must be calculated on a single CT scan encompassing all pertinent OAR.

Table 6.1-1

Metastatic Location	Minimum IGRT Requirement	
	No Fiducials	With Fiducials**
Lung--Peripheral ⁺	Volumetric (3D)	Orthogonal kV (2D)
Lung—Central ⁺	Volumetric (3D)	Orthogonal kV (2D)
Mediastinal/Cervical LN	Volumetric (3D)	N/A
Liver ⁺	Volumetric (3D)	Orthogonal kV (2D)
Spinal	Orthogonal kV (2D)	Orthogonal kV (2D)
Osseous*	Orthogonal kV (2D)	N/A
Abdominal-pelvic ⁺	Volumetric (3D)	Orthogonal kV (2D)

*NOTE: When osseous/rib metastases are classified into another metastatic location, follow the IGRT guidelines for that site.

**NOTE: When a metastasis contains an implanted fiducial that is clearly visible on kV orthogonal or volumetric imaging, either method can be used

+NOTE: Registration using a soft tissue surrogate for the tumor is recommended for lung, liver, and abdominal-pelvic metastases for both 3D and 2D IGRT datasets.

Fig 6.2.1-1. Central lung definition.

[figure not shown]
